12. ADVERSE EVENTS AND DEVICE DEFICIENCIES

12.1 DEFINITIONS

The categories of adverse events are shown in table 12.1-1. The definitions for each of these categories are given in the subsequent sections (see reference within the table).

Table 12.1-1: Categories of Adverse Event

		NOT DEVICE-RELATED		DEVICE- OR PROCEDURE-RELATED	
NON-SERIOUS		ADVERSE EVENT (AE) (SEE 12.1.1)		ADVERSE DEVICE EFFECT (ADE) (SEE 12.1.2)	
SERIOUS	SERIOUS ADVERSE EVENT (SAE) (SEE 12.1.3)	SERIOUS ADVERSE DEVICE EFFECT (SADE) (SEE 12.1.3)		ANTICIPATED UNANTICIPATED	
		ANTICIPATED SERIOUS ADVERSE DEVICE EFFECT (ASADE) (SEE 12.1.4)		UNANTICIPATED SERIOUS ADVERSE DEVICE EFFECT (USADE) (SEE 12.1.4)	

12.1.1 Adverse Event

An Adverse Event (AE) is any untoward medical occurrence between enrollment (signed ICF obtained) and study discontinuation with the use of an IP, whether or not considered causally related to that IP.

AE is used both to refer to AE which are non-serious non-IP or procedure-related and as an umbrella term referring to adverse events of all classifications.

An AE can be any unfavorable and unintended sign (for example, an abnormal laboratory finding), symptom, or disease. For reporting purposes, emphasis is placed first and foremost on whether or not the event constitutes an untoward medical occurrence.

Study Protocol—Device	
Prospective, Multicenter, Post-Market Clinical Follow-up Study to evaluate safety and performance of the SUTUREFIX ULTRA and SUTUREFIX CURVED Suture Anchors in shoulder and hip arthroscopic repair	Number: 17-5010-06
	Version: 1.0, 09/MAY/2018
	Page: Page 52 of 87

12.1.2 Adverse Device Effect

An Adverse Device Effect (ADE) is an adverse event that, in the opinion of the investigator, is related to the IP or the procedure.

Not Related - An AE is considered to be not related to the use of an IP or the procedure when the effect is DEFINITELY UNRELATED or UNLIKELY to have any relationship to the use of the IP or the procedure;

Related - An AE is considered to be related to the use of an IP or the procedure when there is a POSSIBLE, PROBABLE, or DEFINITE relationship between the AE and the use of the IP or the procedure.

An ADE is further categorized depending on whether the criteria in section 12.1.3 and 12.1.4 are met.

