12.1.3 Serious Adverse Events and Serious Adverse Device Effects

An AE or ADE is considered a **Serious** Adverse Event (SAE) or **Serious** Adverse Device Effects (SADE) if, in the view of either the Investigator or the Sponsor, it:

- Results in death.
- Is life-threatening (*NOTE:* The term “life-threatening” in the definition of “serious” refers to an event/reaction in which the subject was at risk of death at the time of the event/reaction; it does not refer to an event/ reaction which hypothetically might have caused death if it were more severe).
- Requires in subject hospitalization or results in prolongation of existing hospitalization.
- Results in persistent or significant incapacity or substantial disruption of the ability to conduct normal life functions.
- Is a congenital anomaly/birth defect.
- Is a medically important event or reaction.

Study Protocol—Device	
Prospective, Multicenter, Post-Market Clinical Follow-up Study to evaluate safety and performance of the SUTUREFIX ULTRA and SUTUREFIX CURVED Suture Anchors in shoulder and hip arthroscopic repair	Number: 17-5010-06
	Version: 1.0, 09/MAY/2018
	Page: Page 53 of 87

Medical and scientific judgment should be exercised in deciding whether other situations should be considered serious such as important medical events that might not be immediately life-threatening or result in death or hospitalization but might jeopardize the subject or might require intervention to prevent one of the other outcomes listed in the definition above. Examples of such events are intensive treatment in an emergency room or at home for allergic bronchospasm, blood dyscrasias, or convulsions that do not result in hospitalization; or development of drug dependency or drug abuse.

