12.1.4 Anticipated/Unanticipated Serious Adverse Device Effect

An Unanticipated Serious Adverse Device Effect (USADE) is a serious ADE that meets any of the above definitions but is also considered, by the Investigator, to be caused by or related to the IP, not previously identified in nature, severity or degree in the IFU ^{28,29,30}.

An Anticipated Serious Adverse Device Effect (ASADE) is a serious ADE that does not meet the criteria for a USADE ^{28,29,30}.

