12.2 REPORTING PROCEDURES

AE of any kind and DevD will be recorded in the applicable CRF and source notes. The Investigator will evaluate all AE for relationship to the device and procedure, if applicable, seriousness, and severity. ADE, SAE, and DevD will be entered into the CRF and reported to the Sponsor within 24 hours of the investigator being informed about the event (Figure 12.2-1). For ADE and DevD, details of the product/procedure related to the event will be included and where applicable, pictures taken of the device. The deficient product should be retained for return to S&N unless it is contaminated (e.g. used dressings must not be retained). Updates to submitted information will be recorded in the CRF within 24 hours of the information being available to the investigator.

[figure not shown]
All SAE and ADE will be reviewed by a medically qualified person appointed by the Sponsor to determine which, if any, meet criteria for expedited reporting to the regulatory authorities.

The investigator will inform the IRB/IEC of adverse events according to the IRB/IEC requirements.

Depending on the nature of the adverse event, S&N may request copies of the subject's medical records, Imaging, Operative notes, as well as results of any relevant laboratory tests performed or other documentation related to the AE. If the subject was hospitalized, a copy of the discharge summary may be requested by S&N and should be forwarded as soon as it becomes available. In certain cases, S&N also may request a letter from the Investigator that summarizes the events related to the case. Refer to the ISF Sponsor Contact Information Sheet to report SAE, unanticipated ADE and SADE, anticipated SADE, and DevD.

Study Protocol—Device	 smith&nephew
Prospective, Multicenter, Post-Market Clinical Follow-up Study to evaluate safety and performance of the SUTUREFIX ULTRA and SUTUREFIX CURVED Suture Anchors in shoulder and hip arthroscopic repair	Number: 17-5010-06
	Version: 1.0, 09/MAY/2018
	Page: Page 55 of 87

Figure 12.2-1: Evaluation and Reporting of AE and DevD

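### Seriousness can be set by the investigator or the Sponsor, but relatedness only by the investigator, so SADE and USADE counts may be too low

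*Combined protocol and SAP*

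**What the plan says.** Section 12.1.3 treats an event as serious "if, in the view of either the Investigator or the Sponsor, it" meets one of the listed criteria. Either opinion is enough.

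Relatedness is worded differently. Under 12.1.2 an ADE "is an adverse event that, in the opinion of the investigator, is related to the IP or the procedure". Under 12.1.4 a USADE is a serious ADE that "is also considered, by the Investigator, to be caused by or related to the IP" and is not already described in the IFU. Section 12.2 agrees: "The Investigator will evaluate all AE for relationship to the device and procedure, if applicable, seriousness, and severity".

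Section 12.1.2 also fixes the cut-off. An event is not related "when the effect is DEFINITELY UNRELATED or UNLIKELY to have any relationship to the use of the IP or the procedure", and related "when there is a POSSIBLE, PROBABLE, or DEFINITE relationship between the AE and the use of the IP or the procedure".

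Section 12.2 then brings in the Sponsor: "All SAE and ADE will be reviewed by a medically qualified person appointed by the Sponsor". The only purpose given for that review is to decide whether an event needs expedited regulatory reporting. The section also requires SAEs, ADEs and device deficiencies to reach the Sponsor within 24 hours.

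Section 10.5 tabulates all adverse events by seriousness, for the whole sample and by device implanted. It specifies no split by relatedness, although the Synopsis lists ADEs, SADEs and USADEs among the safety data.

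**The concern.** The two judgements that define a SADE are made under different rules. A second opinion can raise an event to serious. For relatedness, the definitions recognise only the investigator's opinion. If the investigator rates an SAE as unlikely to be related and the Sponsor's reviewer thinks a link is possible, the protocol does not say how the event is classified or whether the disagreement is recorded.

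This matters more here than in a controlled trial. Section 8.2 describes an open-label study without a control group, so no comparator rate could reveal that events are being attributed away from the device. Section 6.2 has participating surgeons implanting the anchors, and the primary endpoint is surgeon-assessed. An investigator judging causality may therefore often be judging their own operation. The stated aim (8.1) is to confirm safety levels acceptable for the device's risk-benefit profile, and the SADE and USADE categories bear directly on that.

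**Working it through.** The plan gives no figure to reproduce on this point. The check is to set the rules side by side and follow one event through them.

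| Judgement | Who decides | Where |
|---|---|---|
| Seriousness | Investigator or Sponsor; either is enough | 12.1.3 |
| Relatedness for ADE, and so SADE | Investigator | 12.1.2, 12.2 |
| Relatedness for USADE | Investigator | 12.1.4 |
| Need for expedited reporting | Sponsor's medical reviewer | 12.2 |

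**Does 12.1.3 carry over to relatedness?** No. Its phrase "in the view of either the Investigator or the Sponsor" introduces a list made up only of seriousness criteria. A SADE is an ADE that meets one of them, so SADE status still depends on the ADE definition in 12.1.2.

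**One event followed through.** Take an SAE that the investigator rates unlikely to be related.

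1. Under 12.1.2 it is not related, so it is not an ADE and cannot be a SADE or USADE.
2. Under 12.2 it still goes to the Sponsor within 24 hours, because it is an SAE.
3. The Sponsor's reviewer sees it, since the review covers all SAEs.
4. If the reviewer disagrees on causality, the readable text neither allows nor forbids reclassification and gives no rule for settling the matter.
5. In the 10.5 table it is counted as an adverse event and as serious. Only a count by relatedness would miss it.

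**Direction.** Under an either-party rule, the related events are all those the investigator calls related plus any that only the reviewer does. For the reviewed events, that rule can raise the SADE and USADE counts or leave them unchanged. It cannot lower them, and the SAE total stays the same.

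**Scale.** The Synopsis and 7.1 plan 80 subjects, 40 per joint group. For one subject whose SAE moves from not related to related, and who has no other SADE:

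- whole sample: 1/80 = 1.25 percentage points on the SADE subject rate;
- within a joint group: 1/40 = 2.5 percentage points.

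The whole-sample figure matches a denominator that 10.5 uses. The joint-group figure is for orientation only, because 10.5 does not tabulate adverse events by joint. The documents give no expected SAE or SADE rate and no rate of causality disagreement, so the number of such subjects cannot be derived.

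**The case against.** The strongest reply is that little is lost. Every SAE reaches the Sponsor whatever its causality rating, and item 8 of Appendix 21.5 likewise has the investigator report all SAEs to the Sponsor without a relatedness filter. A medical reviewer sees them all. The related category starts at *possible* and covers the procedure as well as the device, which pushes ADE and SADE counts up. Device problems also show in outcomes that do not use the ADE label: failure and re-intervention, anchors pulled out, deployment success, additional anchors and device deficiencies. All of this stands and limits what can be claimed.

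A reader might draw three stronger conclusions that the documents do not support.

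- *That the reviewer is barred from changing relatedness.* No passage says so. Figure 12.2-1, which covers evaluation and reporting of adverse events, is not reproduced in the copy reviewed and may show a further step. The supportable statement is that the readable text gives no such power.
- *That device harm is under-counted.* This is possible but not shown. No disagreement rate is given, an SAE rated unlikely remains in the SAE count, and 10.5 as written has no relatedness table in which it would be missing.
- *That a reportable event can be suppressed.* For SAEs, the expedited-reporting decision belongs to the Sponsor's reviewer, and nothing says that decision is bound by the investigator's rating.

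It is also fair to say that no passage names the operating surgeon as the causality assessor.

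What survives is the asymmetry in the definitions and the lack of a stated rule for disagreement.

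**Conclusion.** The point holds in a limited form. Seriousness may be set by either party, while ADE, SADE and USADE status rests on the investigator's opinion alone, with no stated route for the Sponsor's reviewer to upgrade relatedness. SADE and USADE counts may therefore be too low; total AE and SAE counts are unaffected. Each reclassified subject would add 1.25 points overall or 2.5 points in a joint group, and how many there would be is unknown.

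This rests on three assumptions: that investigators are often the operating surgeons, which is inferred from 6.2 and the surgeon-assessed endpoint; that Figure 12.2-1 adds no Sponsor causality step; and that the planned 80 subjects form the denominator. It is a cheap improvement to the classification rule and does not invalidate the safety analysis.

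**What to change.** For the SAEs and ADEs already reviewed under 12.2:

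- Amend 12.1.2 and 12.1.4 so that an event is related if either the investigator or the Sponsor's reviewer considers it so, matching the rule that 12.1.3 already uses for seriousness.
- State in 12.2 that the reviewer assesses causality, and record both assessments.
- Add to 10.5, and to the detailed SAP that section 10 says is still to be written, a table by relatedness (ADE, SADE, USADE) using the more conservative assessment, with a listing of disagreements.

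Non-serious events that the investigator rates unrelated are neither SAEs nor ADEs and do not reach the reviewer under 12.2. Leave them on the investigator's assessment, so that no extra review is created. The non-serious ADE count then still depends on one opinion, and the report should say so.

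The cost is the wording changes, one added data field, one added table with its listing, and SADE and USADE counts that may rise slightly. Section 12.4.1 ties follow-up of ongoing events to relatedness, so the amendment should also say which assessment applies there.

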12.1.3 Serious Adverse Events and Serious Adverse Device Effects

An AE or ADE is considered a **Serious** Adverse Event (SAE) or **Serious** Adverse Device Effects (SADE) if, in the view of either the Investigator or the Sponsor, it:

- Results in death.
- Is life-threatening (*NOTE:* The term “life-threatening” in the definition of “serious” refers to an event/reaction in which the subject was at risk of death at the time of the event/reaction; it does not refer to an event/ reaction which hypothetically might have caused death if it were more severe).
- Requires in subject hospitalization or results in prolongation of existing hospitalization.
- Results in persistent or significant incapacity or substantial disruption of the ability to conduct normal life functions.
- Is a congenital anomaly/birth defect.
- Is a medically important event or reaction.

Study Protocol—Device	
Prospective, Multicenter, Post-Market Clinical Follow-up Study to evaluate safety and performance of the SUTUREFIX ULTRA and SUTUREFIX CURVED Suture Anchors in shoulder and hip arthroscopic repair	Number: 17-5010-06
	Version: 1.0, 09/MAY/2018
	Page: Page 53 of 87

Medical and scientific judgment should be exercised in deciding whether other situations should be considered serious such as important medical events that might not be immediately life-threatening or result in death or hospitalization but might jeopardize the subject or might require intervention to prevent one of the other outcomes listed in the definition above. Examples of such events are intensive treatment in an emergency room or at home for allergic bronchospasm, blood dyscrasias, or convulsions that do not result in hospitalization; or development of drug dependency or drug abuse.

12.1.4 Anticipated/Unanticipated Serious Adverse Device Effect

An Unanticipated Serious Adverse Device Effect (USADE) is a serious ADE that meets any of the above definitions but is also considered, by the Investigator, to be caused by or related to the IP, not previously identified in nature, severity or degree in the IFU ^{28,29,30}.

An Anticipated Serious Adverse Device Effect (ASADE) is a serious ADE that does not meet the criteria for a USADE ^{28,29,30}.

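### A serious event related only to the procedure and not identified in the IFU is classified as anticipated by default, and the USADE category cannot contain it

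*Combined protocol and SAP*

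**What the plan says.** - **Section 12.1.2** sets the entry condition: "An Adverse Device Effect (ADE) is an adverse event that, in the opinion of the investigator, is related to the IP or the procedure". A possible, probable or definite "relationship between the AE and the use of the IP or the procedure" is enough for an event to count as related.
- **Table 12.1-1** places both the anticipated and the unanticipated serious categories in the column headed "DEVICE- OR PROCEDURE-RELATED".
- **Section 12.1.3** makes an AE or ADE serious "if, in the view of either the Investigator or the Sponsor, it" meets one of the listed criteria.
- **Section 12.1.4** adds two conditions for a USADE. The event must be "considered, by the Investigator, to be caused by or related to the IP, not previously identified in nature, severity or degree in the IFU". The procedure is not mentioned.
- **Section 12.1.4** then defines the other category by subtraction: "An Anticipated Serious Adverse Device Effect (ASADE) is a serious ADE that does not meet the criteria for a USADE".
- **The synopsis** lists USADEs among the safety data. ASADEs are not listed there.

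**The concern.** The words anticipated and unanticipated suggest a split by whether an event was foreseen in a reference document. The definitions do not produce that split. The unanticipated category carries two tests, relation to the device and absence from the IFU, and the anticipated category takes every serious ADE that fails either one. An event can therefore be called anticipated only because it was attributed to the surgery and not to the anchor.

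This can arise in practice, because every subject has an arthroscopic operation and some serious events may be attributed to the operation alone. Confirming an acceptable safety profile is a stated purpose of the study. A USADE count that cannot include unlisted procedural events, beside an anticipated group that can include events no list identified, could mislead a reader of the safety results.

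**Working it through.** No figure in the plan is involved, so the check applies the definitions as logical conditions.

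Conditions, with their sources:

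- ADE = related to the device OR related to the procedure (12.1.2; same scope in Table 12.1-1)
- SADE = ADE AND serious (12.1.3)
- USADE = SADE AND related to the device in the investigator's view AND not identified in the IFU (12.1.4)
- ASADE = SADE AND NOT USADE (12.1.4)

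For a serious ADE this gives four combinations:

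| Relatedness | Identified in the IFU? | Category under 12.1.4 |
|---|---|---|
| Device (with or without procedure) | Yes | ASADE |
| Device (with or without procedure) | No | USADE |
| Procedure only | Yes | ASADE |
| Procedure only | No | ASADE |

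The fourth row is the fault. The event enters as an ADE through the procedure, fails the USADE test because it is not related to the device, and falls into ASADE although the IFU does not identify it. No other section defines anticipated differently for these categories or requires an ASADE to be listed.

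Three further comparisons set the limits of the point.

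- **Reporting and review.** Section 12.2 requires every ADE and SAE to reach the sponsor within 24 hours. It also has all of them reviewed by a medically qualified person for expedited reporting. Entry to that review does not depend on the anticipated or unanticipated label.
- **Planned tables.** Section 10.5 tabulates adverse events by seriousness, overall and by device. It plans no split by anticipated status.
- **Reference list.** Section 12.1.4 names the IFU. Section 4.4 gives a list that it attributes to the IFU and that includes loss of fixation or anchor pullout. The adverse reactions legible in the appended IFU (section 21.1) are inflammatory reaction, foreign body reaction, infection and allergic reaction, without pullout. That page was poorly read from the PDF, so this is a reason to check the original and not evidence of an error.

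**The case against.** The strongest case on the other side accepts the logic and disputes the consequence. Four parts of it stand.

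- A reader might infer that unexpected serious events escape expedited review, or are misplaced in the planned safety tables. The documents do not support either inference. Section 12.2 covers all ADEs and SAEs whatever their label, and section 10.5 has no table in which the label appears. The criteria applied inside the medical review are not stated, so an effect of the label there would be conjecture.
- The affected group is narrow. Under 12.1.2 a merely possible relation to the device counts as related, so an unlisted event with any such link is still a USADE. Only events judged unlikely or definitely not related to the anchor, yet related to the operation, fall into the gap.
- A reader might infer that an event missing from the IFU is by that fact unexpected. It is not. Section 4.1 itself describes surgical complications outside the legible IFU list, such as glenoid osteochondrolysis and heterotopic bone formation. A split by IFU listing alone, extended to procedural events, would label known surgical complications unanticipated, which is the opposite error.
- A reader might see a contradiction in the sponsor having a say on seriousness but not on relatedness. There is none. Relatedness is the investigator's judgement in both 12.1.2 and 12.1.4. The consequence is only that a serious, unlisted event that the sponsor alone relates to the device cannot be a USADE.

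One defence does not stand. It might be said that the device in 12.1.4 is shorthand for device or procedure. Section 12.1.2 names the two separately throughout, and the USADE text names only one, as a condition additional to being a serious ADE.

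**Conclusion.** The point holds as a fault of classification. Under the stated rules, any serious event judged related to the procedure only and not identified in the IFU becomes an ASADE, and the USADE category cannot include it. The scope of Table 12.1-1 and that of the USADE text also disagree.

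The size is limited to the label and to the USADE count named in the synopsis. Reporting to the sponsor, the medical review and the tables planned in 10.5 are not shown to be affected. How many events would be misclassified cannot be derived, because the documents give no rate of serious procedure-only events. The conclusion assumes that 12.1.4 is applied as written and that investigators record relation to the device and to the procedure separately, as 12.2 asks them to.

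**What to change.** 1. Give 12.1.2, Table 12.1-1 and 12.1.4 the same relatedness scope.
2. Define ASADE positively, as a serious ADE identified in nature, severity and degree in one named reference list. Define USADE as a serious ADE, related to the device or the procedure, that is not so identified. The two categories are then exhaustive, do not overlap, and depend on listing alone.
3. Make that reference list cover the anticipated complications of the procedure as well as the device effects in the IFU. Without this, the new definition would label known surgical complications unanticipated.
4. Check the list in 4.4 against the original IFU, in particular the entry for pullout.
5. If the sponsor's view of relatedness is meant to count, change 12.1.2 and 12.1.4 together. A change in 12.1.4 alone would conflict with 12.1.2, which leaves ADE status to the investigator.

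The cost is revised definition wording and a short list of procedural complications. Some events may move to the unanticipated category. No change to the planned analyses is needed.
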